Off-pump CABG is performed to improve cardiac blood flow without the use of a cardiopulmonary bypass machine which may provoke complications including stroke, renal failure, and blood loss. Despite potential benefits, off-pump surgery can cause complications including graft occlusion, myocardial infarction, and neurocognitive deficits. The prevalence of such complications varies widely in the literature, with some studies suggesting it ranges from 5% to 30%, influenced by patient comorbidities and surgical technique. Continuous monitoring of tissue oxygenation may reduce the incidence of such complications by enabling the early detection and correction of tissue hypoperfusion. This approach could lead to more tailored and responsive patient management during and after surgery, potentially improving postoperative outcomes and reducing the overall complication rate associated with off-pump CABG.

Objectives and Endpoints

The following text was from the original protocol registered before the start of the trial.

Primary objective

To establish whether the care guided by cerebral and somatic tissue oxygen saturation monitoring compared to usual care reduces perioperative complications in patients having off-pump coronary artery bypass grafting surgery within 30 days of randomization.

Primary outcome measure

The primary outcome is a collapsed (one or more) composite of the following complications with a Clavien-Dindo grade II or greater arising within 30 days of randomization.

- Brain complications (postoperative delirium, cognition decline, stroke);
- Cardiac complications (non-fatal cardiac arrest, myocardial injury, heart failure, new-onset symptomatic ventricular arrhythmia);
- Respiratory failure;
- Renal complications (AKI stages II and III);
- Infectious complications (surgical site infection involving deep surgical site and/or organ/space, pneumonia, laboratory confirmed bloodstream infection, infection with source uncertain, and sepsis);
- Death.

Secondary objectives

To determine whether the care guided by $SctO_2$ and $SstO_2$ monitoring reduces various complications and duration of hospitalization.

Secondary outcome measures

- Components of the primary composite

- Atrial fibrillation, assessed within postoperative 30 days
- Postoperative delirium assessed from postoperative day 1 to 5
- Postoperative cognitive decline as a continuous variable assessed before surgery and on postoperative days 5 and 30

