Stage	Target Information (%)	N1	N2	Efficacy Boundary (Critical Z-value scale)	Alpha Spent	Futility Boundary	Beta Spent	Power
1	33%	309	309	±3.710	0.0002		0	-

[figure not shown]
2	67%	618	618	± 2.511	0.0119	± 1.157	0.0828	-
3 (final)	100%	927	927	± 1.932	0.0379	± 1.932	0.1172	0.803

Note: O'Brien-Fleming Analog alpha and beta spending function is adopted

The trial could be stopped for efficacy if the efficacy boundary is crossed at first ($Z < -3.71$, $\alpha < 0.0002$) or second ($Z < -2.51$, $\alpha < 0.0119$) interim analysis, respectively (Figure 1). We will evaluate the combined outcome incidence at the first intermediate analysis and increase sample size at that point if it proves to be lower than anticipated.

If the futility boundary is not crossed ($-1.16 < Z < 1.16$) at second interim analysis, and the study will continue if there is no safety concern. If needed, the sample size of the study might be re-estimated by the DSMB statistician using the observed aggregated data (not the treatment effect) using the conditional power analysis at the interim analysis stage. Since the futility boundary is assumed non-binding, even it is crossed, the DSMB will make recommendation on whether or to stop the trial taking in consideration the totality of accumulated evidence, including the patient accrual rate, observed treatment effect, etc. The whole evaluation will be conducted in a blinded manner.

Figure 1. Group sequential plot

Two interim analyses were performed as per the protocol. No stopping rules were triggered and the DSMB recommended continuing at each analysis. Therefore, the trial proceeded and

finished.

Analysis Populations

Intention-to-Treat (ITT) population: All randomized patients having at least some outcome data will be included in the analysis in the groups to which they were randomized, regardless of the care they received.

Per-Protocol (PP) population: This analysis includes patients, as long as they have outcome data, who completed the study in accordance with the protocol. The patient in the intervention group is determined to have received the intended intervention if their NIRS measurements during the intervention time window are within 90-110% of the baseline value for 80% of the time. The purpose is to assess the effect of the intervention under optimal conditions.

[figure not shown]
Documentation of Deviations:

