- All protocol deviations will be documented in a protocol deviation log, which will be reviewed regularly by the trial steering committee to ensure consistency in applying the exclusion criteria.
- The rationale for excluding each participant will be documented in detail.

The primary analyses of the primary and secondary outcomes will be based on the ITT population. The per-protocol population will be used in the safety and sensitivity analysis.

Note: Patients who were randomized and treated, but lost to follow up, will be included to the time of dropout. Patients who withdrew their consent to participate the study will not be included in analysis.

The CONSORT diagram as of January 26, 2024 is presented as follows. The last patient was recruited on December 27, 2023. At the time of formulating this statistical analysis plan, the follow-up per research protocol is ongoing. We anticipated to finish patient follow-up in early February 2024.

We will evaluate the baseline homogeneity using absolute standardized differences. For both primary and secondary analyses, we will correct for baseline factors with ASDs above the threshold determined by the following equation: $1.96 \times \sqrt{(\text{nt} + \text{nc})/(\text{nt} * \text{nc})}$.1 where t is treatment and c is control.

Analysis of the primary outcome

The primary outcome will be evaluated using logistic regression to estimate the odds of postoperative composite complications. A one-sided Z-value < -1.932 will be considered statistically significant.

A sensitivity analysis evaluating an average relative effects model. (Edward J Mascha, Daniel I Sessler. Statistical grand rounds: design and analysis of studies with binary- event composite endpoints: guidelines for anesthesia research. *Anesth Analg*. 2011 Jun;112(6):1461-71. doi: 10.1213/ANE.0b013e31821796d3.)

Analysis of the secondary outcomes

For the secondary analysis of continuous and categorical outcomes in the BOTTOMLINE-CS trial, the following details will outline the statistical methods that will be used. All analyses will be adjusted for unbalanced baseline characteristics and reported with 95% confidence intervals.

- Continuous outcomes will be analyzed using linear regression or generalized linear models as appropriate, depending on the distribution of the data and the study design.
- Composite secondary outcomes will be analyzed using the same approach as the primary outcome.

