- A narrative will be provided to explain the implications of the sensitivity analyses findings in the context of the trial conclusions.

Subgroup Analyses

- The outcomes targeted in the subgroup analyses include all primary and secondary outcomes. Interactions between the intervention and primary outcome will be evaluated for each subgroup. Odds ratio for the primary outcome, as a function of subgroup, will be presented as a forest plot with 95% confidence intervals.
- The subgroup analyses will be based on the following variables:
 - Age (< 65 years vs. \geq 65 years)
 - Sex (male vs. female)
 - BMI (< 30 kg/m² vs. $>$ 30 kg/m²)
 - Blood component transfusion during the study period (yes vs. no)
 - Duration of surgery (< 3 hours vs. $>$ 3 hours)
 - Temperature during surgery (based on each patient's median value, $<$ 35.5 °C vs. $>$ 35.5 °C)
 - Cerebral tissue oxygen saturation (based on each patient's median value, $<$ 70% vs. $>/=$ 70%)
 - Somatic tissue oxygen saturation (based on each patient's median value, $<$ 75% vs. $>/=$ 75%)
 - Cardiac output index (based on each patient's median value, $<$ 3 L/min/m² vs. $>/=$ 3 L/min/m²)
 - Systemic vascular resistance (based on each patient's median value, $<$ 1000 dyn·s·cm⁻⁵ vs. $>/=$ 1000 dyn·s·cm⁻⁵)
 - Heart rate (based on each patient's median value, $<$ 60 bpm vs. $>/=$ 60 bpm)
 - Mean arterial pressure (based on each patient's median value, $<$ 65 mmHg vs. $>/=$ 65 mmHg)
 - End-tidal carbon dioxide (based on each patient's median value, $<$ 30 mmHg vs. $>/=$ 30 mmHg)
 - History of stroke (yes vs. no)
 - History of myocardial infarction (yes vs. no)
 - History of hypertension control (based on pre-operative measurement with the threshold of 140/90 mmHg, (yes vs. no)
 - Antihypertensive medication, (yes vs. no)
 - History of diabetes (based on the preoperative diagnosis, yes vs. no)
 - History of chronic renal disease (based on the preoperative diagnosis, yes vs. no)
 - History of chronic obstructive pulmonary disease (based on the preoperative diagnosis, yes vs. no)
 - Current cigarette smoking (yes vs. no)

Ethical Considerations

The ethical considerations were specified in the protocol registered before the start of the trial.

Quality Control and Data Management

The quality control and data management were specified in the protocol registered before the start of the trial.

Software and Programming

R software (version 4.3.2, R Foundation for Statistical Computing, Australia).

Tables and Figures

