
Creating mock-ups or templates for tables and figures is an essential part of the statistical analysis plan to visualize how the results will be presented. Below are descriptions of the structure and content for the key tables and figures that will typically be included in the results section of a clinical trial report. Please note that actual tables and figures would be created using statistical software and formatted according to the journal or reporting guidelines.

Table 1: Baseline Characteristics of Participants

- This table will present demographic and clinical characteristics of participants at baseline, stratified by treatment groups.
- The table will typically include rows for each characteristic, such as age, sex, BMI, ASA score, comorbidities, and any other relevant baseline measures.
- Columns will be used to display the characteristic's name, the intervention group's data, and the control group's data.
- Standard descriptive statistics will be presented: means and standard deviations for continuous variables; frequencies and percentages for categorical variables. The absolute standardized differences will also be reported.

Table 2: Perioperative Intervention and Relevant Information

- This table will summarize the perioperative interventions, covering both the operative room and intensive care unit periods.
- The table will typically include rows for each intervention or relevant information, such as drugs, fluids, duration of surgery, and mechanical ventilation duration.
- Standard descriptive statistics will be presented: means and standard deviations for

continuous variables; frequencies and percentages for categorical variables. We will report p values depending on the journal style.

Table 3: Primary and Secondary Outcomes Analysis

- This table will summarize the analysis of the primary outcome. Alternatively, and depending on the journal's preference, we can instead present the main results using a forest plot and move the table to supplementary material.
- It will have rows for the outcome measure, the number of events or mean (depending on the nature of the outcome), standard deviation or standard error, and the results of the logistic regression including odds ratios, 95% confidence intervals, and p-values.
- The table will have columns for the intervention group, control group, and the comparison between the two.
- If secondary outcomes are continuous, the table will include mean differences instead of odds ratios.

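### Covariates enter the primary and secondary models only when they happen to be unbalanced, so a modest and nearly free gain in power is left unused

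*SAP*

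**What the plan says.** The rule stands at the end of the SAP section Analysis Populations and covers primary and secondary analyses alike: "we will correct for baseline factors with ASDs above the threshold determined by the following equation". The equation is 1.96 × √((nt + nc)/(nt × nc)). The section on secondary outcomes repeats the principle: "All analyses will be adjusted for unbalanced baseline characteristics and reported with 95% confidence intervals". The section on the primary outcome specifies a logistic regression and the decision rule "A one-sided Z-value < -1.932 will be considered statistically significant", and names no covariate. No other section names one to be kept whatever the balance.

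The SAP itself expects prognostic factors to exist. Its background paragraph describes complications as "influenced by patient comorbidities and surgical technique". The subgroup list shows that age, sex and history of stroke, myocardial infarction, diabetes, chronic renal disease and chronic obstructive pulmonary disease (COPD) are recorded. The nearest thing to a list of candidate factors is the description of the baseline table under Tables and Figures, "such as age, sex, BMI, ASA score, comorbidities, and any other relevant baseline measures". That wording is open-ended, and the adjustment rule does not refer to it.

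On timing, the SAP reports of the two interim analyses that "No stopping rules were triggered and the DSMB recommended continuing at each analysis", and of the data that "At the time of formulating this statistical analysis plan, the follow-up per research protocol is ongoing".

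**The concern.** In a randomised trial any baseline imbalance is due to chance. Selecting covariates by observed imbalance ignores what makes adjustment worthwhile, which is how strongly a factor predicts the outcome. A strong predictor that is well balanced is left out, and an irrelevant factor that is unbalanced comes in.

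Three things follow.

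- The precision that prognostic baseline data could give is mostly not obtained.
- The covariate set is unknown until the allocated data are seen. Because a logistic odds ratio is conditional on its covariates, the quantity estimated varies with chance too.
- The candidate factors and their coding are not closed, so they could be settled after group-wise baseline data are available.

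For cognition, the pre-surgery score is usually the best single predictor one could hope for, yet it is a covariate only if the groups happen to differ on it.

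The stake is efficiency and a primary model fixed in advance. The validity of the test is not in question.

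**Working it through.** **1. What the threshold is.** The formula is from Analysis Populations. The group sizes, 927 for power and 980 recruited, are from Sample Size Determination and the interim-analysis table, which shows 927 in each arm.

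- 1.96 × √((927 + 927)/(927 × 927)) = 1.96 × √(2/927) = 0.0910
- 1.96 × √(2/980) = 0.0885

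An ASD is a difference in means divided by the standard deviation. Under randomisation its standard error is √((nt + nc)/(nt × nc)), so the rule is |z| > 1.96. Each factor enters with probability of about 0.05, whatever its prognostic value. For seven independent factors, P(at least one enters) = 1 − 0.95^7 = 0.302. In about 70% of trials none of the seven enters.

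**2. The plan's own power.** Drift = 0.06/√(0.30 × 0.70/927 + 0.24 × 0.76/927) = 2.916. With looks at one third, two thirds and the end, efficacy boundaries 3.710, 2.511 and 1.932, and the second-look futility boundary of 1.157 obeyed, power is 0.810. The SAP gives 0.803. If futility is ignored, power is 0.841. This power involves no covariates.

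**3. Power under three analyses.** The simulation used 12,000 trials per scenario, 927 per group and marginal risks of 30% and 24%.

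- Assumed factors: age (normal), sex 25%, stroke 10%, myocardial infarction 20%, diabetes 30%, renal disease 5%, COPD 5%, all independent, plus 11 irrelevant candidates open to the rule.
- Assumed strengths (odds ratio per binary factor / log odds ratio per SD of age) are in the first column. The joint AUC runs from 0.50 to 0.76.

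Single final test, P(Z < −1.932):

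| Strength | Unadjusted | SAP rule | Fixed set | Fixed minus rule (points) |
|---|---|---|---|---|
| 1.0 / 0 | 0.839 | 0.838 | 0.838 | 0.1 |
| 1.25 / 0.15 | 0.832 | 0.831 | 0.837 | 0.6 |
| 1.5 / 0.25 | 0.833 | 0.833 | 0.850 | 1.6 |
| 2.0 / 0.25 | 0.838 | 0.841 | 0.865 | 2.5 |
| 2.0 / 0.40 | 0.839 | 0.843 | 0.873 | 3.0 |
| 3.0 / 0.55 (extreme) | 0.830 | 0.836 | 0.899 | 6.4 |

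Differences are taken before rounding; their Monte Carlo standard error is 0.10 to 0.25 points. The rule differs from no adjustment by −0.2 to +0.6 points.

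Gain of the fixed set over the rule, in points, with interims taken as unadjusted:

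| Odds ratio per binary factor | 1.0 | 1.25 | 1.5 | 2.0 | 3.0 |
|---|---|---|---|---|---|
| Whole three-stage design, futility obeyed | 0.1 | 0.4 | 1.0 | 1.6 | 3.5 |
| Final test, given continuation past both interims | 0.1 | 0.8 | 2.3 | 3.6–3.7 | 8.0 |

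Continuation means a second-look Z between −2.511 and −1.157. Unadjusted three-stage power in these runs was 0.80 to 0.81.

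**4. Checks.** A smaller repeat (3,000 trials per scenario) gave single-test gains of 0.1, 0.7 and 2.7 points and three-stage gains of −0.1, 0.3 and 1.4 points at odds ratios 1.0, 1.5 and 2.0. A different structure (ten independent normal covariates, 3,000 trials, single final test) gave these powers for unadjusted / rule / fixed:

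- R² about 0.05: 0.841 / 0.839 / 0.856
- R² about 0.10: 0.844 / 0.850 / 0.877
- R² about 0.15: 0.846 / 0.850 / 0.898

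**5. Type I error.** In the single final test with 30% in both arms and strength 2.0 / 0.40, rejection was 0.0276 unadjusted, 0.0253 with the rule and 0.0284 with the fixed set. The nominal value is Φ(−1.932) = 0.0267. There is no sign of inflation from any of the three.

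**6. Equivalent sample size.** From the single-test results the gain equals 3.8–4.7% more patients at odds ratio 1.5 and 7.4–10.3% at 2.0. Of 2 × 927 = 1,854 that is about 70 to 190 patients.

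**7. Cognition.** Take equal variances before and after surgery and correlation r. In units of that variance, the residual variance is 1 − r² with the baseline score as covariate, 2(1 − r) for a change score and 1 for the follow-up score alone. The saving is (1 − r)/2 against a change score: 25% at r = 0.5 and 15% at r = 0.7. Against the follow-up score alone it is r²: 25% and 49%. Both values of r are assumed.

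**The case against.** The case for leaving the rule alone is a fair one. It is an explicit formula, it looks only at baseline data, it does not inflate type I error, and it preserves the power that the design was sized for. Nothing in the SAP is contradicted. The gain rests on prevalences, odds ratios and independence that the SAP does not supply. Over the whole design it is 1.6 points even if all six binary factors double the odds. The background remark on comorbidities explains why complication rates vary between reports; it does not measure patient-level prognosis. The proposed model also moves the odds ratio away from the marginal contrast of 30% against 24%. Finally, the SAP never says that cognitive decline is a change score, so a saving against a change score may have no target.

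Most of this stands as a limit on size. The gain must be given as a range that includes zero, and the three-stage figures are the right measure of the design as a whole. The patient-equivalent figures come from a single test and carry the same assumptions. The 70% figure concerns the seven named factors only; with 18 independent candidates, 1 − 0.95^18 = 60% of trials would admit at least one of something.

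It does not remove the point. Both interims are past, so the final test is the decision that remains, and there the gain is larger. For cognition, the baseline score as covariate is at least as efficient as either possible outcome definition. The shift in the odds ratio is handled by reporting the unadjusted one as well.

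**Conclusion.** The point holds as an efficiency not taken, and it should be changed. Observed imbalance is the only route into the models. It gives each factor about a 5% chance of entry and buys less than one point of power over no adjustment. A fixed set of factors already collected would gain from essentially zero up to about 1.6 points over the three-stage design, and up to about 3.7 points in the final test now remaining, for assumed odds ratios up to 2.0 per binary factor. The larger figures at odds ratio 3.0 describe an extreme case. Confidence in the direction is high. Confidence in the size is moderate, because prognostic strength is assumed throughout and the smaller repeat gave lower gains at odds ratio 1.5. A benefit that needs no assumption about strength is that the primary model would be known before the allocated data are seen.

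**What to change.** Before unblinding, name a fixed set of baseline covariates for the primary logistic model, used whatever the observed balance. One example is age, sex, and history of stroke, myocardial infarction, diabetes, chronic renal disease and COPD. About 500 expected events (27% of 1,854) support seven covariates comfortably. State the coding of each. Always include the pre-surgery cognitive score in the cognition model. Keep ASDs in the baseline table as description. Keep the imbalance-adjusted model as a sensitivity analysis with a closed list of candidate factors.

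The cost is SAP wording; no new data are needed, and follow-up was still running when the SAP was written. The one drawback is interpretive. The fixed-set odds ratio is conditional on the named covariates: about 0.73 at assumed odds ratio 1.5 and 0.71–0.72 at 2.0, against a marginal (0.24/0.76)/(0.30/0.70) = 0.737. That is a larger shift than the imbalance rule causes, so the unadjusted odds ratio should be reported beside it.

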The pragmatic trial design selected for the BOTTOMLINE-CS trial is rooted in its focus on evaluating the effectiveness of multisite tissue oxygen saturation monitoring in a real-world clinical setting. This approach emphasizes the applicability of the trial outcomes to typical clinical scenarios by ensuring that the study conditions closely mimic everyday practice. Unlike explanatory trials, which often employ strict participant selection and controlled conditions to determine efficacy under ideal circumstances, a pragmatic trial embraces broader eligibility criteria and diversity in participant characteristics, mirroring the variability seen in daily medical care. Furthermore, the implementation of interventions and monitoring within the usual care processes enables the assessment of the intervention's practical impact, including its feasibility, adherence, and overall utility in routine clinical workflows. The findings from such a pragmatic study are likely to be generalizable and thus informed clinical decision-making.

Sample Size Determination

The following paragraph was from the original protocol registered before the start of the trial. "We assume that the incidence of the composite 30-day complication in the regular care group will be 30% versus 24% in the multisite tissue oxygenation-guided perioperative care group, a 20% relative reduction representing a clinically meaningful and important treatment difference. Based on one-sided Z-test group sequential testing with 3 stages (two interim analyses) and boundary values calculated from O'Brien-Fleming Analog alpha (efficacy) and non-binding beta spending (futility) functions, a total of 927 patients will provide 80% power for detecting a 6% absolute reduction from 30% to 24% at a target alpha-level of 0.05. We plan to recruit 980 patients per group considering a potential ~5% of patients who drop out or have missing data."

Interim Analysis

The following is from the original protocol established before the start of the trial.

"For the interim analyses, O'Brien-Fleming Analog alpha and beta spending functions are used (Table 1, Figure 1). Assuming two interim analyses occur after 33% and 67% of total patients are enrolled and their primary outcome are observed, the nominal alpha levels to reject the null hypothesis for efficacy or fail to reject the null hypothesis for futility are calculated as follows.

Table 1. Critical values and alpha levels for two interim analyses and final analysis

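### The final critical value of 1.932 assumes binding futility although the SAP declares futility non-binding (which gives 1.993), and the stated one-sided 0.05 contradicts the 0.025 per tail behind Table 1

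*SAP*

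**What the plan says.** - **Level and sidedness.** Sample Size Determination describes a one-sided group sequential Z-test with three stages, giving "80% power for detecting a 6% absolute reduction from 30% to 24% at a target alpha-level of 0.05".
- **Futility.** The same paragraph specifies O'Brien-Fleming "Analog alpha (efficacy) and non-binding beta spending (futility) functions". Interim Analysis repeats the point: "Since the futility boundary is assumed non-binding, even it is crossed, the DSMB will make recommendation".
- **Bounds.** Table 1 has looks at 309, 618 and 927 per group. The efficacy bounds are ±3.710, ±2.511 and ±1.932, with alpha spent of 0.0002, 0.0119 and 0.0379. The futility bound at look 2 is ±1.157, and power is 0.803.
- **Final rule.** Analysis of the primary outcome: "A one-sided Z-value < -1.932 will be considered statistically significant".
- **Look 2.** Interim Analysis gives the condition for continuing as "If the futility boundary is not crossed ($-1.16 < Z < 1.16$) at second interim analysis", and later reports "No stopping rules were triggered and the DSMB recommended continuing at each analysis".
- **Reporting.** The description of results Table 3 promises "the results of the logistic regression including odds ratios, 95% confidence intervals, and p-values".

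**The concern.** A non-binding futility bound earns no alpha credit. The efficacy bounds must hold the error rate even if a crossed futility bound is overridden, so they are computed with futility ignored. A final bound below 1.96 after two efficacy looks at two-sided 0.05 suggests that credit was taken. The ± bounds and a spending total of 0.05 in Table 1 also sit badly with a test described as one-sided at 0.05 and carried out in the lower tail only.

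Two ranges of the final Z are affected. Between -1.993 and -1.932 the trial would be declared positive without meeting the 0.025 per tail that Table 1 spends. Between -1.932 and -1.695 it would be declared negative although the result meets the one-sided 0.05 stated in words. The document does not show which error rate is intended. Follow-up was still under way when the SAP was written, so the rule could still be settled before the final analysis.

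**Working it through.** **Inputs.** From Table 1: information times 1/3, 2/3 and 1 (309, 618 and 927 per group), interim bounds 3.710 and 2.511, look-2 futility bound 1.157. From Sample Size Determination: event rates 30% and 24%. Boundaries come from recursive numerical integration of the joint distribution of the three Z statistics.

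**1. Which alpha produced Table 1?** The O'Brien-Fleming-type spending function is α(t) = 2[1 − Φ(z₁₋α/₂ / √t)].

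- At 0.025 per tail, cumulative spending is 0.0001035, 0.0060484, 0.0250. The increments are 0.0001035, 0.0059449, 0.0189516; doubled, they are 0.0002, 0.0119, 0.0379. This is Table 1 to rounding.
- At one-sided 0.05, the increments are 0.0007, 0.0157, 0.0336 and the bounds with futility ignored are 3.200, 2.141, 1.695. None of these is printed.

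Table 1 is therefore a two-sided 0.05 design, 0.025 per tail.

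**2. Which futility assumption gives 1.932?** Solve for the final bound c that brings the lower-tail error to 0.025, keeping 3.710 and 2.511:

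| Treatment of \|Z₂\| < 1.157 | Final bound |
|---|---|
| Ignored (non-binding) | 1.993 |
| Always stops (binding) | 1.9325 |
| Printed | 1.932 |

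The printed figure is the binding one.

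**3. Error of the printed rule** (3.710 / 2.511 / 1.932, lower tail):

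- Futility not enforced: 0.0001 + 0.0060 + 0.0223 = 0.0283 (before rounding of the terms), or 0.0567 over both tails.
- Futility always enforced: 0.0250.
- With 1.993 and futility not enforced: 0.0250.

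The excess is 0.0283 − 0.0250 = 0.0033, and 0.0033 / 0.0250 ≈ 13%. The Z window is 1.993 − 1.932 = 0.061. If the looks actually fell anywhere from 30%/60% to 35%/70% (an assumed range), the lower-tail error of 1.932 is 0.0281 to 0.0288, and the corrected bound is 1.988 to 2.002 with the interim bounds kept.

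**4. The literal one-sided 0.05.** With the interim bounds used, a final cut-off of 1.695 gives a one-sided error of 0.0460, and the cut-off that spends exactly 0.05 is 1.654. Against that level 1.932 is conservative.

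**5. Power.** The drift at 927 per group is 0.06 / √[(0.30×0.70 + 0.24×0.76)/927] = 2.916 (2.910 with pooled variance). Unpooled results:

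| Final bound | n per group | Futility ignored | Futility followed |
|---|---|---|---|
| 1.932 | 927 | 84.1% | 81.0% |
| 1.993 | 927 | 82.6% | 79.9% |
| 1.993 | 980 | 84.6% | 82.1% |

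The printed 0.803 lies within one percentage point of the 81.0% for 1.932 with futility followed. Pooled variance lowers each entry by at most 0.2 points. A true one-sided 0.05 design (3.200 / 2.141 / 1.695) at 927 per group would have 89.3% power with futility ignored, and 84.8% with the printed 1.157 followed. The stated 80% therefore also points to 0.025 per tail.

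**6. The look-2 sentence.** In Table 1 the interval from -1.157 to 1.157 is the futility region, since it holds the results furthest from either efficacy bound. The text describes the same interval as futility not crossed. The two readings are opposite, so the report that no stopping rule was triggered does not show on which side of 1.157 the second-look Z lay.

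**The case against.** The strongest reply is that the only alpha stated in words is one-sided 0.05, and at that level 1.932 gives at most 0.0283. On that reading no stated error rate is breached. This is correct, and the excess exists only against 0.025 per tail. But every printed bound and increment belongs to 0.025 per tail, and the interim bounds in Table 1 were set at that level, so the literal reading cannot be reconciled with the table.

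The excess is also a ceiling. It assumes that a crossed futility bound would always be overridden; if always followed, the error is 0.0250, and DSMB discretion puts the truth between the two. That stands as a statement about size. It does not rescue 1.932, because a design declared non-binding must control error at the ceiling. The report that no stopping rule was triggered does not help either: the bound is a property of the design, not of the path the trial took.

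Finally, Table 1 is quoted from the protocol, and changing a primary threshold after two interim analyses is a formal amendment. This is fair and bears on how the fix is recorded. The SAP nevertheless adopts 1.932 as its own decision rule, so the error governs the primary test.

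**Conclusion.** The concern holds. The final critical value contradicts the declared non-binding futility rule, and the stated level contradicts Table 1. On Table 1's own spending the non-binding value is 1.993. Using 1.932 raises the lower-tail error from 0.0250 to at most 0.0283. This rests on looks at 1/3 and 2/3 of the information, O'Brien-Fleming-type spending (which reproduces the table), and 0.025 per tail as the intended level. If one-sided 0.05 was truly intended, there is no inflation, but then the interim bounds, increments and final value in Table 1 are all wrong for that design. Numerically the effect is modest. It should still be corrected before the final analysis, because it concerns the sole threshold for the primary claim.

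**What to change.** Before the final analysis, in a dated SAP amendment justified by the stated design alone:

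1. State sidedness and alpha once, at 0.025 per tail to match the interim bounds used, and align Sample Size Determination and Analysis of the primary outcome with Table 1.
2. Replace 1.932 by 1.993 in Table 1 and in the primary decision rule, or recompute the final bound from the actual interim information with futility ignored.
3. Reconcile the look-2 sentence with Table 1, and say which reading underlies the statement that no stopping rule was triggered.
4. Update the printed power of 0.803 to match the corrected bound.
5. Preferably, report the odds ratio with an interval that matches the threshold beside the planned 95% interval. For 1.993 the level is 2Φ(1.993) − 1 = 95.4%. Otherwise a Z of -1.97 would be non-significant with a 95% interval that excludes 1.

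The cost is one number, one alpha statement and a few sentences, with no additional patients. The threshold becomes slightly stricter: at 927 per group with futility followed, power falls from 81.0% to 79.9%; at the planned 980 it is 82.1%.
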